- **Children (Subpart D / 21 CFR 50.55):** Assent will be obtained from all participants capable of understanding the study. Materials will be written at an age-appropriate level, and staff will ensure that youth comprehend their right to decline participation without penalty.
- **Juvenile Prisoners (Subpart C):** The protocol ensures participation will not affect probation status, privileges, or case outcomes, and no coercive incentives will be offered.
- **Confidentiality:** Journals and questionnaires will be de-identified. Data will be stored securely on HIPAA-compliant servers, accessible only to the study team.
- **Risk/benefit balance:** The Heal intervention is non-invasive, brief, and aligned with existing therapeutic activities. Risks are no greater than those ordinarily encountered in detention settings, while potential benefits include improved emotional regulation, therapeutic alliance, mental health outcomes and coping strategies.
- **Continued care:** Since the participants in this study are receiving on-going care even after the conclusion of this trial, follow-ups on progress will continue with the clinical staff.

Exclusion Criteria

- **Age:** Juveniles younger than 12 years or older than 18 years at the time of clinical trial enrollment.
- **Custody/length of stay:** Juveniles with an anticipated remaining detention stay of less than 8 weeks, as determined by facility records
- **Clinical instability**
 - Active suicidal ideation with plan or intent
 - Uncontrolled psychosis, mania, or other acute psychiatric condition requiring immediate intervention
 - Severe cognitive or developmental impairment preventing meaningful participation in the Heal sessions, journaling or drawing, or standardized assessments
- **Medical contraindications**
 - History of seizure disorders triggered by light, music, sound, vibration or sitting in confined spaces
 - Severe sensory impairments such as profound hearing or vision loss that would prevent exposure to the intervention
 - Any other acute medical condition, as determined by facility clinicians, that would compromise the participant's safety
- **Language/comprehension:** Juveniles unable to understand study instructions in basic level English.

- **Safety risks in custody:** Juveniles who present a current, significant risk of violence toward themselves or others who cannot be safely managed within the Healpod environment

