This study does not involve administration of drugs, biologics, food, cosmetics, or regulated devices. The Healpod is a non-invasive, non-medical, sensory-guided intervention tool that uses commercially available speakers and bass shakers to deliver sound and gentle vibration.

End of Study Activities

Study Completion Criteria: The study will be considered complete once all participants complete the 8-week intervention, final assessments are collected, and any protocol deviations/adverse events are resolved.

End-of-Study Visit: At week 8, participants will:

- Complete final assessments (MAIA-Y, DERS-16, TASC-R, PHQ-9, GAD-7, PSS-4, and KidCOPE).
- Submit final journals.
- Participate in a debriefing to review study purpose and confirm voluntary participation.

Data Management: All collected data will be de-identified, scanned, coded, and analyzed according to the statistical analysis plan and per HIPAA regulations.

Participant Communication: Participants will be thanked for their contributions. Summaries of results may be shared with participants, parents/guardians or LARs, and facility staff as appropriate.

Archiving and Retention: All records, including consent forms, journals, and therapist assessments, will be securely archived for a minimum of 7 years, per regulatory requirements.

Study Closure: After data analysis, reporting, and archiving, the study will be formally closed with submission of a final report to the IRB and any relevant authorities.

Safety Management

Safety Plan

Definitions

- **Adverse Event (AE):** Any unfavorable or unintended psychological or physical effect that occurs during the study, whether or not it is related to the Heal intervention
- **Serious Adverse Event (SAE):** Any event that results in death, is life-threatening, requires hospitalization, or causes significant disability
- **Severity of Events:** Categorized as mild, moderate, or severe, based on the extent of disruption to normal activities
- **Unanticipated Problems (UPs):** Any incident or outcome that is unexpected, related or possibly related to the intervention, and suggests greater risk to participants or others than previously known
- **Events of Special Interest:** Heightened agitation, severe emotional distress, or behavioral escalation during or after the Heal session
- **Relatedness:** Events will be classified as unrelated, possibly related, or definitely related to the Heal intervention

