- **Expectedness:** Events will be judged as expected (e.g., mild drowsiness, transient emotional responses) or unexpected (e.g., extreme agitation, panic)

Safety Monitoring and Reporting

Participants will be monitored throughout the study for physical, psychological, and behavioral safety as needed. Since the participating juveniles will be in custody, such monitoring will be easy to do on an as-needed basis. Juvenile Hall staff and study clinicians will remain present and observe participants during their Heal sessions through the Healpod observation window, ensuring immediate response to any visible distress.

- **AE monitoring:** All AEs will be documented using a standardized AE reporting form. Examples of possible AEs include emotional upset, refusal to continue, or reports of increased anxiety.
- **SAE reporting:** Any SAE will be reported immediately or within 24 hours to the Principal Investigator (PI) and forwarded to the WCG IRB.
- **Unanticipated problems:** Other unanticipated problems will be reported promptly, but no later than 7 days, to the IRB, together with a proposed corrective action plan.

Risk Mitigation

To reduce potential risks to the juveniles enrolled in this study, the following steps will be undertaken:

- **Informed consent/assent:** Participants and parent/guardian/LAR will be informed of possible emotional changes and reassured of their right to stop participation at any time.
- **Screening procedures:** Clinical staff will confirm psychiatric stability before enrollment to minimize risk of harm and will continue to monitor participants at every session for any associated changes.
During the initial screening, participants will be asked whether they are currently pregnant. If so, they will not be enrolled in the study. Staff will also remind participants to inform the research team if they become pregnant at any point during the study so they can be safely withdrawn.
- **Emergency protocols:** Facility mental health staff and probation officers at the SLO County Juvenile Hall will be immediately available in the event of participant distress.
- **Session design:** Heal sessions are brief (~5 minutes), non-invasive, and similar to simply listening to music, which is already permitted in Juvenile Hall; these elements of the intervention reduce risk exposure.
- **Ongoing monitoring:** Clinicians will review participants' journals and post-session reflections for signs of distress that might require follow up.

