- **Post-trial monitoring:** participants in this study will continue receiving on-going care even after the conclusion of this trial. Follow-ups on how they feel with the intervention post-clinical trial will continue with the clinical staff.

This risk mitigation and safety expectation is supported by empirical data from the SLO County Behavioral Health 4-Year Innovation Evaluation (2021-2025), which documented **zero adverse or serious adverse events** in > 1,100 adult Heal sessions, even among participants with significant mental-health comorbidities. These findings justify treating the present juvenile study as **minimal risk**, with expected AEs limited to mild, transient emotional responses (e.g., tearfulness, relaxation fatigue).

Data Safety Oversight

Given the minimal-risk nature of this behavioral intervention:

- The PI will review all safety reports monthly.
- Facility clinical staff will conduct immediate debriefing for any participant exhibiting distress.

Pregnancy Reporting and Follow-Up

This study does not include pregnant participants, if a pregnancy is discovered during the study, it will be documented and reported. The participant will no longer stay eligible or continue in the research study. No inducements, monetary or otherwise, will be offered to terminate a pregnancy. Individuals engaged in the research will have NO part in any decisions as to the timing, method, or procedures used to terminate a pregnancy. Individuals engaged in the research will have no role in determining the viability of a neonate.

Subpart C: Prisoner Protections

Because participants are detained youth, they qualify as “prisoners” under 45 CFR 46 Subpart C. To ensure compliance with these provisions, this study is structured as follows:

- Participation is voluntary, and refusal or Discontinuation will not affect probation status, privileges, or access to services.
- Risks are minimal, limited to mild emotional change comparable to ordinary daily life in custody. Any risks arising from the Heal intervention are further mitigated since youths will meet with their therapist directly after every Heal session for ~15 to 30 minutes of therapy.
- The research presents a reasonable probability of direct benefit to participants by improving their emotional regulation, therapeutic alliance, mental health and coping skills.

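### Self-harm or a suicide attempt treated inside the facility can fall outside both the SAE definition and the unanticipated-problem definition, leaving it with no reporting deadline

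*Protocol*

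**What the plan says.** The Protocol, under Safety Management (Safety Plan, Definitions), gives an SAE four limbs: "Any event that results in death, is life-threatening, requires hospitalization, or causes significant disability". The same list defines an unanticipated problem as one that is "unexpected, related or possibly related to the intervention, and suggests greater risk to participants or others than previously known". It defines Events of Special Interest as "Heightened agitation, severe emotional distress, or behavioral escalation during or after the Heal session".

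Safety Monitoring and Reporting attaches deadlines to two of these categories. For the first, the text reads: "Any SAE will be reported immediately or within 24 hours to the Principal Investigator (PI) and forwarded to the WCG IRB". For the second, the IRB must hear within a week of any problem in that class that is not already covered.

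Other adverse events go on a standard form, with no time limit for passing it on. No time is given for Events of Special Interest as a category. Data Safety Oversight adds: "The PI will review all safety reports monthly". Safety Monitoring Analysis, in the statistical section, promises reporting of SAEs and unanticipated problems and adds no further category or deadline.

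Self-harm appears only in the Introduction, as an outcome of an earlier programme in detained youth. Suicidality appears only among the Exclusion Criteria ("Active suicidal ideation with plan or intent"), next to an exclusion for risk of violence to self or others that cannot be safely managed in the Healpod.

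**The concern.** Participants are detained minors with, or at risk of, mental health or substance use disorders. The exclusion on suicidality covers active ideation with a plan or intent. Lesser ideation and past self-harm are not excluded by that item, so self-harm during the study is foreseeable.

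The setting also makes on-site handling likely. Under Risk Mitigation, mental health staff and probation officers are on hand at once if a youth is in distress. An act can therefore be contained and treated without a hospital admission, and admission is one of only four ways to become an SAE.

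Two things are at stake. The investigator and the IRB might learn of such an event late, or the IRB not at all by any stated route. And the SAE count could be zero although such an event had occurred. Numbers of AEs and SAEs are a named outcome in the Summary (Exploratory Objectives), in Variables and Endpoints, and in Exploratory Analyses. Study Purpose and Analytic Frame makes safety part of the primary aim.

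**Working it through.** No sample size or power figure is involved. The check is to route a self-harm act or suicide attempt through every category that the Protocol defines.

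**Inputs.** The SAE, unanticipated-problem, expectedness and Events of Special Interest definitions (Safety Plan, Definitions); the reporting times (Safety Monitoring and Reporting); the monthly review (Data Safety Oversight); 8 weeks of participation (Key Design Features).

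**Routing.**

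| Features of the event | Category | Stated time |
|---|---|---|
| (a) Fatal, life-threatening, hospitalized or significantly disabling | SAE | At most 24 hours to the investigator, then the IRB |
| (b) None of (a), but unexpected **and** at least possibly related **and** suggesting greater risk | Unanticipated problem | At most 7 days to the IRB |
| (c) None of (a), and failing at least one condition of (b) | Ordinary AE | Form without deadline; monthly review |

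**Can a self-harm event land in (c)?**

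1. *Failing (a).* An attempt that is stopped early, or an injury treated on site, can be neither life-threatening, hospitalized nor disabling.
2. *Failing (b) on expectedness.* Not realistically. The Definitions and Risk Mitigation confine expected events to mild, transient reactions, so self-harm would be unexpected.
3. *Failing (b) on relatedness.* Yes. An act attributed to custody, trauma or an existing disorder can be rated unrelated.
4. *Failing (b) on greater risk.* Yes. This is a separate judgement, and all three conditions must hold.

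So (c) is not empty, and steps 3 and 4 are the ways into it.

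**Do Events of Special Interest catch it?** The category does not name self-harm, is tied to the Heal session, and carries no reporting time of its own.

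**Length of the wait.** Take a month as 28 to 31 days (an assumption) and suppose that the event falls just after a review and nobody reports it sooner. The wait is then up to 28 to 31 days, against 1 day in (a) and 7 days in (b). Participation lasts 8 × 7 = 56 days, so this is 28/56 = 50% to 31/56 = 55% of one youth's time in the study.

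**Effect on the counts.** An event in (c) enters the AE counts by type, severity, relatedness and expectedness. It adds nothing to the SAE count.

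**The case against.** The other side has good points, and they set the limits of this one.

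- **Serious attempts are already covered.** A life-threatening attempt, or one that leads to hospitalization, is an SAE wherever it was first handled. A reader might infer that suicide attempts in general escape the 24-hour route; the definition does not support that.
- **Self-harm cannot readily be dismissed as expected.** A reader might think that self-harm could be called expected because it is common among detained youth. The Protocol ties expectedness to mild, transient responses and lists extreme agitation and panic as unexpected. A possibly related act that suggests greater risk would reach the IRB within 7 days.
- **Care is not delayed.** Clinical staff monitor at every session, clinicians review journals for distress, and a distressed youth is debriefed immediately. It would be wrong to infer that sessions run on unexamined until the investigator's review.
- **The month is a worst case.** The Protocol does not say that forms reach the investigator only at the monthly review, and nothing forbids earlier reporting.
- **Events of Special Interest are not wholly without a route.** One that also qualifies as an SAE or an unanticipated problem takes that route. Only the category itself lacks a time.
- **The tabulation is not at fault.** Exploratory Analyses lists counts for all AEs, so the event would be visible there. Finer layout may properly be left to an analysis plan.

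What survives is the residual group (c). No section of the Protocol gives it a deadline or counts it as serious.

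**Conclusion.** The point holds in a narrow form. With only four limbs in the SAE definition, self-harm or a suicide attempt that is treated on site, is not life-threatening or disabling, and is judged unrelated or not suggestive of greater risk has no stated deadline for reaching the investigator and no stated route to the IRB. The worst-case wait for the investigator's review is about a month, and the event is not counted as an SAE.

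This rests on three assumptions: that such an event can be managed without hospitalization, that the rater uses the categories as written, and that no one reports earlier than required. How often such events would occur cannot be derived from the Protocol, and no rate is claimed. The SAE definition and its reporting times are fixed in the Protocol itself, so this is not a matter left to an analysis plan. The change is worth making because it bears on a stated outcome in a vulnerable population and is cheap.

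**What to change.** 1. In Safety Plan, Definitions, extend the SAE definition with: *or any suicide attempt, self-harm needing medical attention, or other important medical event, wherever it is treated*. These events then follow the existing 24-hour route and enter the SAE count, with no new procedure.
2. In Safety Monitoring and Reporting, state a time within which Events of Special Interest are reported to the investigator. The length is for the sponsor to set. The category includes agitation and behavioural escalation, and the Introduction reports that roughly 61% to 70% of confined youth are easily upset, often angry or hot-tempered, so a 24-hour rule for all of them could generate many reports.

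The cost is a few sentences in the safety section and possibly a few more expedited reports. Care, session delivery and the planned AE counts are unchanged.

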- **Emotional regulation:** DERS-16 will be administered in read-aloud format for participants whose literacy is limited
- **TASC-R:** measures child-therapist therapeutic alliance
- **Stress, anxiety, depression:** PHQ-9, GAD-7, and PSS-4 will be administered in read-aloud format for participants whose literacy is limited
- **Coping skills:** KidCOPE will be administered in read-aloud format for participants whose literacy is limited.

- **Intervention phase (Weeks 1-8 in custody)**

- **Dose/frequency:** For participating juveniles, 1 to 2 Heal sessions per week will be scheduled prior to their regular therapy appointments.
- **Client session journal:** Participating juveniles will complete journal entries or drawing after each Heal session.
- **Heal Therapist Assessment form:** Therapists will fill out the Therapist Assessment form after each therapy session with a participating juvenile.
- **Modality**
 - **Sensory-guided intervention (Healpod):** Each 5-minute Heal session provides the following non-verbal somatic/ experiential/ sensory experiences inside the Healpod:
 - Curated calming music/soundscapes, such as slow tempo 60-80 BPM nature sounds
 - Optional vibroacoustic delivery of gentle vibrations, operated per the Healpod safety parameters and approved by the facility
 - **Expressive writing/journaling or drawing:** Following the session in the HealPpd, participants will complete very brief journaling or drawing to capture their feelings post-session,
- **Bi-weekly (Week 2±1, 4±1, 6±1)**
 - Repeat PHQ-9, GAD-7, PSS-4 (read-aloud if needed)
 - Check for willingness to continue
- **Mid-point (Week 4 ±1):**

- Repeat MAIA-Y, DERS-16, TASC-R, PHQ-9, GAD-7, PSS-4, and KidCOPE
- Check for willingness to continue

- **End-of-custody participation (Week 8 or pre-release/transfer):**
 - Repeat MAIA-Y, DERS-16, TASC-R, PHQ-9, GAD-7, PSS-4, and KidCOPE
 - Extract facility incident data during study window where needed
 - Conduct exit interview with probation or clinical staff (≤10 minutes)
- **Early release/transfer:**
 - Collect available end-of-participation measures prior to departure
 - If withdrawal occurs due to pregnancy, available end-of-participation measures will be collected when feasible.

Administration of Drug/Devices/Food/Cosmetics

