A target enrollment of no more than 18 participants reflects practical feasibility, given the facility population, expected length of stay, and consent requirement, and aligns with early-phase pilot norms. This sample is not designed to provide definitive efficacy testing; instead, it will yield effect-size estimates and variance parameters that will guide formal power calculations for a subsequent trial.

Primary Analyses

- **Primary endpoint (Emotional Regulation):**
Change in DERS-16 from Baseline to Week 8 will be the primary analysis.
- **Mechanism (Interoceptive Awareness):**
Change in MAIA-Y (Baseline, Week 4, Week 8) will be analyzed in parallel to test whether interoceptive awareness improves alongside DERS-16.
- **Therapeutic Alliance (Proximal clinical relevance):**
Change in TASC-R (Baseline to Week 4 to Week 8)

Secondary Analyses

- **Therapeutic alliance (detail):** Beyond the primary association analysis, report TASC-R domain-level changes (if scored) with paired tests and effect sizes.
- **Mental health symptoms: PHQ-9, GAD-7, PSS-4** (Baseline, Weeks 2/4/6/8).

Exploratory Analyses

- **Coping skills:** shifts in adaptive vs. maladaptive domains where applicable. KidCOPE scores (Baseline, Week 4, Week 8).

- Adverse events (AEs), and serious adverse events (SAEs): All AE's/SAE's will be documented and compiled into the analytic dataset. We will measure "counts and percentages" by event type (emotional, sensory, physical), severity (mild, moderate, severe), relatedness to the Heal intervention (unrelated / unlikely / possible / probable / definite) and expectedness (expected / unexpected)

Missing Data

Because some youth may be released, transferred, or choose to withdraw before completing the study, missing data are expected. To address this, this study will:

- **Use of all available data:** Analyses will include every data point that participants provide, even if they do not complete all sessions or the full 8-week period.
- **Handle incomplete cases:** If a participant is missing end-of-study data, their last available score will be carried forward as a sensitivity check to confirm whether results are consistent.
- **No complex imputation:** Given the small sample size, advanced statistical methods such as multiple imputation will not be used.
- **Transparency:** Results will be presented with clear notes about how many participants provided data at each timepoint, so that findings can be interpreted in light of attrition.

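### Finding adverse events between Heal sessions is left to discretion, so the count of all AEs may be incomplete and a low or zero count could not be read as evidence of safety

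*Protocol*

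**What the plan says.** **What is to be counted.** Safety Plan, Definitions, makes an AE "Any unfavorable or unintended psychological or physical effect that occurs during the study, whether or not it is related to the Heal intervention". Events of Special Interest in the same list include behavioural escalation after a session as well as during it. Under Exploratory Analyses, "All AE's/SAE's will be documented and compiled into the analytic dataset", with counts and percentages by type, severity, relatedness and expectedness. Study Purpose and Analytic Frame names safety in the primary aim; Variables and Endpoints lists AEs and SAEs as exploratory outcomes.

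**How events are to be found.** Safety Monitoring and Reporting sets the general rule: "Participants will be monitored throughout the study for physical, psychological, and behavioral safety as needed". It adds that, because the youths are in custody, "such monitoring will be easy to do on an as-needed basis". Under Risk Mitigation, clinical staff "will continue to monitor participants at every session for any associated changes", and clinicians review "journals and post-session reflections for signs of distress that might require follow up". In Study Procedures and Timeline, the end-of-custody entry reads "Extract facility incident data during study window where needed".

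**How events are to be recorded.** "All AEs will be documented using a standardized AE reporting form". SAEs go to the principal investigator immediately or within 24 hours, and the investigator reviews safety reports monthly.

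**The concern.** The count is meant to be all-cause and to cover the whole 8 weeks. The means of finding events are fixed for the Heal session and discretionary for the rest of the time. Two sites or two staff members who follow this text to the letter could produce different AE counts from the same events.

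This matters because the protocol already treats an absence of recorded events as evidence. Under Risk Mitigation, zero events in more than 1,100 adult sessions are used to justify minimal-risk status. A low or zero count in this study would invite the same reading and would be carried into the larger trial that the pilot is meant to inform. An event that nobody asked about or looked up cannot be recovered at analysis.

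**Working it through.** The protocol states no expected AE rate, AE count or detection rate, so there is no figure to reproduce and no arithmetic that would size the problem. The check is to take each contact or source in the protocol and ask three things: is it fixed, can it reach the time between sessions, and does the text make it yield an AE record?

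| Source (section) | Fixed? | Reaches time between sessions? | Leads to an AE record in the text? |
|---|---|---|---|
| Observation through the window (Safety Monitoring and Reporting) | Yes | No, about 5 minutes per session | For visible distress, through the AE form |
| Clinician monitoring at each session (Risk Mitigation) | Yes | Not stated; directed at associated changes, which is narrower than the all-cause definition | No inquiry specified |
| Journal review (Risk Mitigation) | Yes | Possibly; entries record feelings after the session | No; the stated purpose is follow-up care |
| Therapist meeting of 15 to 30 minutes, with form (Study Visits; Therapy Integration) | Yes, 1 or 2 times a week | Possibly; nothing restricts the conversation | No; the form is described as covering engagement, regulation and openness |
| PHQ-9, GAD-7, PSS-4 (Schedule of Assessments) | Yes, Weeks 2, 4, 6 and 8 | Partly: depression, anxiety and stress, but not behavioural escalation or physical effects | No rule links a worse score to an AE |
| Continuing consent and willingness checks (Consenting; Study Procedures and Timeline) | Consent checks ongoing; willingness checked bi-weekly and at mid-point | Possibly | No; the subject is willingness |
| Exit interview of up to 10 minutes; debriefing (Study Procedures and Timeline; End of Study Activities) | Yes, once | Possibly | No AE content stated |
| Facility incident records (Study Procedures and Timeline) | No; discretionary, no criterion | Yes, the whole study window | Not stated |

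The standardized form and the monthly review are not in the table because they act only on events that someone has already recognised.

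No source passes all three tests. The one source that is kept independently of the Heal visits and spans the whole period, the incident record, is also the one left to discretion. For SAEs the 24-hour rule, together with custody, makes omission much less likely. What remains exposed is the non-serious event between sessions, including the escalation after a session that the protocol itself singles out as of special interest.

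**The case against.** The strongest reply is that these youths are in custody, with clinical and probation staff on hand, and meet a therapist once or twice a week. Symptom scales follow every two weeks, and the protocol's own examples of an AE include reports of increased anxiety. Consent is re-checked on a continuing basis and noted by staff. It is also fair that the AE form, therapist form, session journal and interview guide are not in the document. One can say only that the protocol text lists no AE inquiry, not that none will be asked. All of this stands, and it limits the point to a risk.

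A reader might infer more: that between-session events are found only by chance, or that the AE count is bound to be too low. The documents do not support either. The contacts above may surface earlier events, and no detection rate is given.

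A reader might also try to size the gap from the small share of the 8 weeks spent in visits, or from an assumed detection rate. Neither measures it. A question asked during a visit can cover the whole interval since the last one, so hours under observation are not ascertainment; and an assumed detection rate only returns what was put in.

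The remaining reply is that wording of this kind belongs on case report forms, and that AEs are exploratory outcomes without inferential testing. The exact question can indeed sit on a form. But the protocol itself sets discretion as the rule for monitoring and for incident extraction, and a descriptive count still has to be complete to be interpretable.

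**Conclusion.** The point holds as a mismatch between an all-cause, whole-period AE count and between-session ascertainment that is discretionary. The consequence is a possible undercount of non-serious events between sessions, of a size that cannot be estimated from the document. A low or zero count could not be read as evidence of safety, because it could reflect how events were looked for. The conclusion rests on the protocol text alone; if the unseen forms already carry a standard AE question at each visit, the first part of the fix reduces to saying so in the protocol. It should be settled before enrolment, since the analysis cannot repair it.

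**What to change.** 1. In Safety Monitoring and Reporting, replace the discretionary rule with one standard open question on any unwanted effect since the last contact. Ask it at every Heal visit, record yes or no on the existing Heal Therapist Assessment form, and repeat it at the end-of-participation contact. A yes leads to the standardized AE form.
2. In the end-of-custody entry of Study Procedures and Timeline, make incident extraction apply to every participant over the whole study window. Site staff, who hold the linking log, should do it under study ID, so that it fits the data-minimization rules. Each incident is screened against the AE and Events of Special Interest definitions.
3. In Exploratory Analyses, report AEs by source: asked, observed, incident record.

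The cost is one item on a form already completed after each therapy session, plus one records extraction and screening per youth. That is a small amount of extra site work. The all-cause count will probably rise. With no control group and no pre-enrolment comparison period, it should be reported descriptively and not attributed to the intervention.
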